
2. Protocol Narrative

a. Aims & Methodology

[figure not shown]
- a) **Aim 1:** To determine the effects of VLNC vs. NNC cigarettes on cigarettes smoked per day and frequency of alternative tobacco product use in adolescent cigarette smokers. We hypothesize that use of VLNC cigarettes will be associated with a decrease in combustible cigarettes smoked per day and an increase in the number of days of alternative combustible and noncombustible tobacco product use.
- b) **Aim 2:** To determine the effects of VLNC cigarettes on nicotine and toxicant exposure, perceived health risk of tobacco products, respiratory symptoms and dependence. We will test the hypothesis that use of VLNC cigarettes will lead to reduced nicotine and toxicant exposure, dependence, and respiratory symptoms in adolescent MTP users.
- c) **Aim 3:** To leverage real-time EMA assessment to determine the effects of VLNC cigarettes on withdrawal and craving, and to determine whether these momentary changes influence alternative tobacco use. We hypothesize that VLNC cigarette exposure may influence momentary changes in withdrawal and craving; and that these will vary both within and across individuals.

Impact of nicotine reduction on adolescent cigarette use, alternative tobacco use, and harm from tobacco

PIs: [name] & [name]

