- d. **Informed consent procedure:** Adolescents who meet initial eligibility criteria, and who remain interested after hearing a more detailed description of the study, will provide contact information for their parent or legal guardian (minors only) so that parental informed consent can be obtained; 18-19 year olds can provide their own informed consent (see **18+ Consent** attachment). Research staff will call the minor's parent/guardian and provide the study information and answer any questions that they have (see **Parent Phone Script** attachment). If parents are willing to consent to their child's participation, we will mail or email them a consent form to sign (and one to keep), which the adolescent participant will bring to the first session (see **Parental Consent** attachment). Eligible interested adolescents (with verbal parental consent if minors) will be scheduled for the initial in-person session and transportation arranged if necessary (see **Adolescent Assent** attachment).

4. Screening

- a. During the initial in-person screening, participants will complete several questionnaires and have their CO taken to confirm eligibility to enroll. Female participants will also submit a urine sample to test for pregnancy. Urine will be sampled for cotinine levels if necessary. The Timeline Follow back, stages of change, and MINI suicide subscale will be used to determine eligibility. We estimate that we may need to consent up to 200 adolescents to result in a final sample of N=120.

b. Inclusion Criteria

- 1) Ages 15-~~19~~20 inclusive
- 2) Male and female current daily smokers
 - a. Defined as self-reported daily cigarette smoking at phone screening AND

Impact of nicotine reduction on adolescent cigarette use, alternative tobacco use, and harm from tobacco

PIs: [name] & [name]

- b. a breath carbon monoxide (CO) criterion of 5 ppm or higher; if this is not met, urine cotinine levels, detected by a NicAlert cotinine screening device, must indicate recent smoking (level 3 or higher)
- 3) Current users of alternative tobacco product(s)
 - a. Defined as any self-reported use of at least one non-cigarette tobacco product (e.g., e-cigarettes, little cigars, cigarillos, hookah, etc.) in the past 30 days
- 4) Participants must speak and comprehend English well enough to complete study procedures.
 - a. Participant will be asked to read aloud first few lines of informed consent and then summarize the contents aloud to check for competency

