b-c. Post-Session COVID survey and qualitative interview: Following the last sessions, participants will be asked if they would like to participate in a short survey and interview. They will first complete a brief survey of their COVID-19 experiences. Then, the researchers will conduct a recorded qualitative interview about their experiences with the EMA app in order to improve future app use.

11. Outcomes, Measures Justification, Descriptions, and Schedule

Primary Outcomes

- Cigarettes smoked per day
- Amount of total alternative product (ATP) use

Secondary Outcomes

- Amount of combustible and amount of noncombustible ATP use
- Toxicant exposure (total nicotine equivalents and NNAL)
- ~~FEV outcomes~~

Exploratory Outcomes

- ATSQ score
- Perceived Health Risk Questionnaire
- Nicotine dependence score
- Differences in craving across time and product type
- Differences in withdrawal across time and product type
- Measures of reinforcing efficacy/cigarette demand from the Cigarette Evaluation Scale
- Hypothetical Purchasing in the Experimental Tobacco Marketplace

Impact of nicotine reduction on adolescent cigarette use, alternative tobacco use, and harm from tobacco

PIs: [name] & [name]

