- b. **Safety:** Pregnancy tests will be performed for all female participants at Screening/BL1, BL2, and both lab visits (weeks 2 and 4). The **suicide subscale** from the Mini International Neuropsychiatric Interview (MINI; Sheehan et al., 2010) will be used at Screening to evaluate suicide risk. CO level will be obtained at every session to evaluate level of exposure to smoke; a large increase in CO (i.e., CO > 80 ppm) can be a reason for withdrawing a participant from the study. **Brief Medical History** (Screening/BL1) assesses physical and emotional health to establish eligibility for participation (determined by the medical monitors). In subsequent sessions, the **Health Changes Questionnaire** asks whether the participant experienced any changes in his/her physical or emotional health since their last visit, including whether they have visited the doctor, the hospital, or whether they have had a change in any of their medications. Any endorsement of a negative health change will be tracked as an adverse event.
- c. **Frequency of tobacco and other drug use measures:** Past 30-day tobacco product use will be comprehensively assessed using a **Timeline Follow-Back (TLFB)**, a reliable calendar-assisted interview validated for estimating daily use of tobacco and other substances in adolescents (Lewis-Esquerre et al., 2005). The TLFB will determine: # cigarettes per day; frequency of e-cig use (including nicotine concentration in e-liquid) and use of all other tobacco products; use of alcohol (# standard drinks/day); and frequency of marijuana use and other illicit or recreational drug use. The TLFB will also be used to assess tobacco, alcohol, marijuana and other drug use between sessions to evaluate use over the course of the study.
- d. **Biomarkers. Expired breath CO** level is a reliable and valid assessment of recent smoking and will be measured using a Vitalograph CO Monitor. CO will be assessed at BL to confirm

Impact of nicotine reduction on adolescent cigarette use, alternative tobacco use, and harm from tobacco

PIs: [name] & [name]

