MR4						How many non-study cigarettes did you smoke yesterday?	Numeric (integer) entry (0-200)	

Morning Report	First Random Prompt Report of the Day (FR)	Random Prompt Report (RR)	Usual Brand Smoke Report (UR)	Study Cig Smoke Report (SR.)	Alternative Product Report (AR)	Item	Response Format	Logic
MR5						Select all alternative tobacco products you used yesterday.	0=None 1=E-cigarette/vape 2=Cigar/cigarillo (Black & Mild, Swisher Sweets) 3=Smokeless tobacco (chew, dip, snuff, snus) 4=Hookah 5=Pipe (tobacco)	Each endorsed choice brings up data entry for quantity (6A-6E)
MR6A						About how many puffs of E-cigarette/vape do you think you took?	Numeric (integer) entry (0-200)	Show only if "E-cigarette/vape" is selected in MR5
MR6A1						Did you finish a Juul pod or refill your vape tank?	0=No 1=Yes	Show only if "E-cigarette/vape" is selected in MR5
MR6B						About how many cigars did you smoke?	Numeric (integer) entry (0-200)	Show only if "Cigar/cigarillo" is selected in MR5
MR6C						About how much smokeless tobacco did you use?	Text entry	Show only if "smokeless tobacco" is selected in MR5
MR6D						About how much hookah did you use?	Text entry	Show only if "hookah" is selected in MR5
MR6E						About how much pipe (tobacco) did you use?	Text entry	Show only if "pipe (tobacco)" is selected in MR5

Morning Report	First Random Prompt Report of the Day (FR)	Random Prompt Report (RR)	Usual Brand Smoke Report (UR)	Study Cig Smoke Report (SR.)	Alternative Product Report (AR)	Item	Response Format	Logic
	FR0A	RR0A				Have you used tobacco in the last 30 minutes?	0=No 1=Yes	If “Yes”, proceed to R0B. If “No”, proceed to R1.
	FR0B	RR0B				Did you do a smoke report?	0=No 1=Yes	If “Yes”, proceed to R1. If “No”, proceed to R0C.
	FR0C	RR0C				Please do a smoke report now.	(Instruction)	All – random survey end.
	FR1					Think about the time since you woke up this morning. Did you forget to enter any smoke reports?	0=No 1=Yes	If “Yes”, proceed to FR1B. If “No”, proceed to FR2.
		RR1				Think about the time since you last completed a report. Did you forget to enter any cigarette or tobacco reports?	0=No 1=Yes	If “Yes”, proceed to R1B. If “No”, proceed to R2.
	FR1A	RR1A				What time did you last use tobacco?	1=15 mins ago 2=30 mins ago 3=45 mins ago 4=1 hour ago 5=2 hours ago 6=3 or more hours ago	

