Cover page for Data Analysis Plan

NCT03860077

Grant number: R01DA047356

Grant Title: Impact of Nicotine Reduction on Adolescent Cigarette Use, Alternative Tobacco Use, and
Harm From Tobacco

Document date: 9/1/23

Data Analytic Approach and Power.

Overview and justification. Mixed effects models evaluated change in total cigarette use, alternative tobacco product use, study cigarette use, and biomarkers of nicotine exposure from baseline to the final study week. All analyses were with SAS V9.4 software (SAS Institute Inc., Cary, NC, USA, 2016). Due to data-collection disruptions related to the COVID-19 pandemic and intermittent data-collection challenges with the ecological momentary assessment (EMA) program, we elected to utilize the most complete data stream for primary analyses, which was Time Line Follow Back (TLFB) of outcomes collected at Week 4 and Baseline. Consistent with our prior work (e.g., ¹), aggregated timeline follow-back (TLFB) data from the final week of study cigarette use (i.e., Week 4) was compared to a one-week baseline period during which participants used usual brand cigarettes (i.e., Baseline). The mixed effect model using TLFB data was chosen over other possible analytic approaches (e.g., ANCOVA with baseline outcome covariates) to reduce bias stemming from (1) pre-randomization group differences in baseline outcome levels, and (2) missing outcome data.

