2. Frequencies of alternative product use (ATP) were low, particularly for combustible ATP use. Therefore, for the primary ATP outcome, combustible and non-combustible ATP use were modeled jointly and recoded as a dichotomous outcome (0 = <7 combined days of ATP use; 1 = 7+ combined days of ATP use), with a binary distribution and log link.
3. As secondary outcomes and to evaluate sensitivity, combustible and non-combustible ATP use were also considered independently as separate outcomes. Frequencies of combustible ATP use at Week 4 were too low to allow for model convergence. Frequencies of non-combustible alternative product use (ATP) were bimodal with peaks at 0 (no use) and 7 (daily use). Therefore, this outcome was recoded as a dichotomous outcome (0 = non-daily non-combustible ATP use; 1 = daily non-combustible ATP use) with a binary distribution and log link.
4. The study cigarette secondary outcome was modeled with a normal, Gaussian distribution. Baseline (Time = 0) in this analysis was average number of usual brand cigarettes at baseline,

prior to randomization, and Week 4 (Time = 1) was the average number of study cigarettes at Week 4.

5. Biomarker outcomes (i.e., total nicotine equivalents [TNEs] and cotinine) were modeled with normal, Gaussian distributions.

Missing data and sample size considerations. Missing data were assumed missing-at-random² (Whittaker, Pituch, & McDougall, 2014). Under the missing-at-random assumption, missing data for each focal variable is not expected to be related to that variable itself, e.g., a missed outcome assessment was not related to what that value would have been if it were assessed³ (Enders, 2006). The mixed model approach utilizing SAS software implemented restricted maximum likelihood estimation (continuous outcomes) and pseudolikelihood estimation (count and binary outcomes) to account for missing data. The mixed model reduces bias relative to other common approaches, particularly in cases where Group size is unbalanced due to attrition and/or baseline outcome levels differ between randomization groups.

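### The primary alternative-tobacco test registers only whether participants reach 7 undefined combined days, so a null result cannot be read as no increase in days of use

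*SAP*

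**What the plan says.** **Protocol.** Section 2a, Aim 1, hypothesises that VLNC cigarettes will bring "an increase in the number of days of alternative combustible and noncombustible tobacco product use". Section 11 lists "Amount of total alternative product (ATP) use" as a primary outcome and "Amount of combustible and amount of noncombustible ATP use" as a secondary outcome. Inclusion criterion 3 (section 4b) requires only "any self-reported use of at least one non-cigarette tobacco product" in the past 30 days, so occasional users can enter. Section 11c describes the Timeline Follow-Back (TLFB) as "a reliable calendar-assisted interview validated for estimating daily use of tobacco", so days of use should be recoverable.

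**SAP.** The overview says that the primary analyses use "aggregated timeline follow-back (TLFB) data from the final week of study cigarette use", set against a one-week baseline. Item 2 of the analysis section gives low frequencies, chiefly of combustible ATP, as the reason for taking both kinds together as one variable, "recoded as a dichotomous outcome (0 = <7 combined days of ATP use; 1 = 7+ combined days of ATP use". It states a binary distribution with log link. Item 3, meant partly as a sensitivity check, reports that the combustible model did not converge. It also reports that non-combustible days peaked at 0 and 7 and were split into daily versus non-daily. The focal test throughout is Group by Time.

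**The concern.** The question in Aim 1 is about days; the test is about a threshold. A test of the share at 7+ asks whether more participants reached 7. It does not ask whether use became more frequent. Movement to other tobacco products is one of the trial's two primary questions, and the lay summary says the work is meant to inform policy. If VLNC smokers moved from occasional to frequent but not daily ATP use, the primary test would not register it.

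Two gaps make this harder to judge. Item 2 does not define combined days, so the primary variable cannot be rebuilt from the SAP. Its stated reason, low frequencies, explains why the outcome was recoded but not why the cut is at 7.

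**Working it through.** **1. The SAP's own power figures.** The SAP gives power of .74 for an estimate of .15 and .96 for .20, with 60 per group, for continuous EMA outcomes. Reading the estimates as standardised mean differences, power = Φ(d√(60/2) − 1.96), which gives Φ(0.82 − 1.96) = 0.13 and Φ(1.10 − 1.96) = 0.19. A change score with an assumed correlation of 0.95 has SD √(2 × 0.05) = 0.316 and gives 0.74 and 0.93. The SAP does not state the scale, SD, correlation or number of occasions, so the figures can be neither reproduced nor called wrong. The point does not depend on them. They do not cover a binary TLFB outcome at the reduced sample size.

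**2. What the coding can see.** Let c and k be the combustible and non-combustible days in the week, each 0–7.
- Sum reading: S = c + k, range 0–14.
- Distinct-days reading: D lies between max(c, k) and min(7, c + k).

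On either reading a combined count below 7 forces k < 7. A participant below 7 at both times is therefore coded 0 at both times in item 2 and in item 3. For anyone with no combustible use, the two codes are the same variable. Item 3 therefore cannot recover a rise that item 2 misses below 7. Example: 1 to 6 days on one product type is 0 → 0 in both models.

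**3. How much the definition matters.** Under the sum, 64 − 28 = 36 of the 64 (c, k) pairs reach 7+, and in 21 of those neither type is used daily. Code 1 needs 2D ≥ 7, so at least 4 distinct days; code 0 allows up to 6. Thus 4, 5 or 6 distinct days can be coded either way. Both types on the same 4 days is coded 1, while one type on 6 days is coded 0. Same-day use is plausible: the morning report asks "Select all alternative tobacco products you used yesterday" and accepts several answers.

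**4. Possible increases (a < b), counted equally.** These are possible moves, not observed ones.
- 0–7 scale: 28 pairs. The 7+ split registers the 7 with b = 7 and misses 21. Four categories (0, 1–3, 4–6, 7) miss 3 + 3 = 6.
- 0–14 scale: 105 pairs. The split registers 7 × 8 = 56 and misses 49 (21 wholly below 7, 28 wholly at or above it).

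**5. Illustration of power.** Every input is assumed, because the documents give none. Days of 0–7 at Baseline and Week 4 come from a latent bivariate normal with correlation 0.7. There are 50 participants per arm and 500 runs. The shares at 0 / 1–6 / 7 days are 40/25/35, 55/25/20 or 60/15/25%. The models are random-intercept logit (7+) and cumulative logit (four categories), with a likelihood-ratio test of Group by Time. Ranges are over the three distributions.

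| Assumed VLNC effect | 7+ split | Four categories |
|---|---|---|
| none | 0.04–0.07 | 0.04–0.06 |
| 15% jump to daily use | 0.17–0.22 | 0.15–0.21 |
| 25% jump to daily use | 0.30–0.44 | 0.32–0.45 |
| general shift, 0.5 latent SD | 0.36–0.48 | 0.59–0.66 |
| 30% of those at 0–3 days rise to 4–6 | 0.06–0.07 | 0.20–0.31 |
| 50% of those at 0–3 days rise to 4–6 | 0.05–0.06 | 0.36–0.60 |

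The last two rows are blind to the 7+ split by construction. They show what would be missed, not how likely it is.

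**The case against.** The cut at 7 has a sensible basis. Item 3 reports peaks at 0 and 7 for non-combustible use, and combustible use was too rare to model alone. A total made of a bimodal part and a rare part should look mostly like the bimodal part. Jumps to daily use fit those peaks best, and there the split loses nothing material. By contrast, the 50% row (with days 1–6 split evenly) would put about 39–46% of Week 4 VLNC participants at 4–6 days, against 20–35% at 7 under the same three distributions. That fits the reported shape poorly. The simulation also uses a logit link and numerical integration, whereas the SAP states a log link and pseudolikelihood. All of this stands, and it limits the size of the point. It does not remove it, because the combined distribution is not reported and the blindness below 7 follows from the coding alone.

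A reader might infer more than the documents support:
- *That the cut was chosen with the arm results in view.* The SAP says that the approach was revised after the distributions were examined. Nothing shows that arm results were known.
- *That sub-daily increases leave no trace anywhere.* This holds for the ATP models that give an estimate. Total nicotine equivalents cover all nicotine products and could partly reflect added ATP use, though they also fall with VLNC smoking and cannot isolate it. The form of the non-converged combustible model is not stated.
- *That the SAP concludes there was no substitution.* It draws no such conclusion. The point concerns how a null may be read.
- *That combined days should be redefined as distinct days.* The SAP is written in the past tense. If a sum was used, redefining it would recode an outcome already analysed and discard part of the total amount that the protocol names.

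**Conclusion.** The concern holds in this form: no ATP model that yields an estimate can register an increase that stays below 7 combined days, and combined days is undefined. A null on item 2 supports only no detected difference between arms in change in the share at 7+ combined days. It does not support no increase in ATP days. A significant 7+ result would remain valid evidence about that share.

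The practical size is unknown. It ranges from no material loss (jumps to daily use) through 14–30 points of power (a general shift) to near-total loss (rises to 4–6 days only). These figures rest wholly on assumed distributions, correlation, effects and 50 per arm. This should be fixed, chiefly because the remedy is cheap and the question is primary.

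**What to change.** 1. Keep the 7+ analysis as run. State in item 2 whether combined days is a sum over product types or distinct days, and why 7 was chosen, noting that the choice followed inspection of the distributions. Do not redefine the variable.
2. Add one analysis, labelled post hoc, that keeps the ordering of days: for example, a cumulative-logit mixed model of Group by Time on TLFB days under the stated definition, with categories such as 0, 1–3, 4–6 and 7+, merged if sparse. Report ATP days by group at Baseline and Week 4; the SAP names descriptive summaries for baseline data only. If the definition is a sum, distinct days with any use can be shown as a supplementary count.
3. Limit any conclusion about substitution to what both analyses show.
4. State the link actually fitted for items 2 and 3. A log link gives risk ratios and a logit link odds ratios, so the meaning of the estimate depends on it.

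Cost: a few sentences in the SAP and one model on TLFB data already collected. Downsides: one more post hoc result, a proportional-odds assumption to check, and possibly sparse middle categories. Under a sum, the top category would still pool 7 to 14.

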Analyses to address project aims. To address primary aims, 2-group (VLNC & NNC) x 2 repeated measures (Baseline & Week 4) mixed effects models tested the effect of the randomization group (VLNC vs. NNC) on change in cigarette use and alternative tobacco product (ATP) use from Baseline to Week 4. Similarly, to address secondary aims related to biomarkers of nicotine exposure, 2 x 2 mixed models tested the effects of VLNC vs. NNC cigarettes on change in biomarkers of nicotine exposure (i.e., total nicotine equivalents [TNEs] and cotinine), as well as average number study cigarettes smoked per day relative to average number of usual brand cigarettes smoked per day. In all models, Group (VLNC = 1; NNC = 0) was a between-subjects predictor, and Time (Baseline vs. Week 4) was the repeated measure. Subject was treated as a random effect to account for subject-level differences in baseline outcome levels. The focal tests evaluated the difference in change from Baseline to Week 4 (i.e., Time) in the VLNC vs. NNC condition (i.e., Group), which is a cross-level interactive effect of Time and Group. A *p*-value < 0.05 was interpreted as meeting statistical significance criteria. For all estimation

parameters, we report effect estimates, standard errors, and 95% confidence intervals in addition to p values.

Consistent with the original statistical analysis plan, demographics and baseline data on participant tobacco use history and individual characteristics were summarized using univariate descriptive statistics (e.g., means, standard deviations, frequencies). Data visualization and formal statistical evaluation of means, standard deviations, skewness, and kurtosis, assessed the distributional characteristics of each outcome. Where the assumptions of models implementing a normal (Gaussian) outcome distribution were not met, the statistical approach was revised accordingly. The following analytic procedures were required to meet model assumptions and account for skewed outcome distributions and low frequency events for certain outcomes.

1. Average cigarettes per day was positively skewed, with a non-normal residual distribution in a mixed model analysis specifying a normal (Gaussian) outcome distribution. Therefore, this outcome was recoded to integers and modeled as a count with a negative binomial distribution and log link.

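### The binary ATP models state a log link under pseudo-likelihood: read literally, probabilities can exceed 1; read as logit, the test is conservative; and no fitted ATP analysis uses days

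*SAP*

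**What the plan says.** In the SAP, under Analyses to address project aims, item 2 merges combustible and non-combustible ATP use and dichotomises it ("1 = 7+ combined days of ATP use), with a binary distribution and log link"). Item 3 treats non-combustible use alone in the same way ("1 = daily non-combustible ATP use) with a binary distribution and log link"). Every model is 2 groups by 2 occasions, and "Subject was treated as a random effect to account for subject-level differences in baseline outcome levels". The missing-data section names "pseudolikelihood estimation (count and binary outcomes) to account for missing data" and states that "Missing data were assumed missing-at-random". The word logit does not appear.

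The reasons given for recoding are low frequencies (item 2) and, for non-combustible use, peaks at 0 and 7 days (item 3). The recoding followed inspection of the distributions: "Where the assumptions of models implementing a normal (Gaussian) outcome distribution were not met, the statistical approach was revised accordingly". On sensitivity, item 3 says "As secondary outcomes and to evaluate sensitivity, combustible and non-combustible ATP use were also considered independently as separate outcomes"; it then reports that the combustible model did not converge and that the non-combustible outcome was dichotomised at daily use.

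Protocol section 2a states the Aim 1 hypothesis as a rise in the number of days of ATP use, and section 11 lists the amount of total ATP use as a primary outcome.

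**The concern.** This model carries one of the two primary outcomes and the trial's product-substitution question. The SAP promises that "we report effect estimates, standard errors, and 95% confidence intervals in addition to p values", but a reader cannot tell what the estimate is. A log link would give a risk ratio; a logit link would give an odds ratio, subject-specific or close to population-averaged depending on the estimation method.

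Each reading of the link has a cost. A log link with a normal subject effect puts no ceiling on the probability. A logit link fitted by pseudo-likelihood to two binary records per person gives standard errors that are too large, and the SAP says the sample was already reduced.

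Separately, the hypothesis is about days, while both ATP models that were fitted see only a threshold. If participants given VLNC cigarettes take up ATP on some days of the week, those models may miss it, and a null result could be misread as no substitution.

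**Working it through.** **The plan's own figure.** The SAP states power of .74 at an estimate of .15 and .96 at .20, with 60 per group. The implied standard errors are .15/(1.960 + 0.643) = 0.0576 and .20/(1.960 + 1.751) = 0.0539. With no variance, intraclass correlation or number of assessments given, these cannot be reproduced. They also concern continuous EMA outcomes, so they say nothing about this binary test.

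**Inputs.** From the SAP: two occasions, subject random effect, pseudo-likelihood, 5% level, planned 60 per arm. Not given, so assumed: prevalence of the 7+ category (0.4, or 0.2 where shown), subject SD, final N (60 or 40 per arm) and effect size.

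**Reading 1: log is literal.** For mean prevalence p and normal subject effect with SD s, the share of people with implied probability above 1 is 1 − Φ((0 − (ln p − s²/2))/s).
- p = 0.4: s = 0.5 gives 1 − Φ(2.08) = 1.9%; s = 0.75 gives 1 − Φ(1.60) = 5.5%; s = 1 gives 1 − Φ(1.42) = 7.8%.
- p = 0.2: 0.0%, 0.6% and 1.7%.

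Fixing the median rather than the mean at 0.4 gives 18% at s = 1, but the implied mean is then 0.4 × e^0.5 = 0.66.

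**Reading 2: log means logit.** Simulation: logit-normal random intercept, 40% at baseline and throughout in NNC, subject-specific log-OR 1.5 (or 0 for the null), 60 per arm, 1,000 runs per scenario. It was programmed outside SAS, with restricted pseudo-likelihood and the residual scale fixed at 1.

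| Subject SD | 1 | 2 | 3 |
|---|---|---|---|
| NNC staying in the same category | 60% | 71% | 78% |
| Power, pseudo-likelihood | 0.62 | 0.42 | 0.23 |
| Power, quadrature | 0.67 | 0.57 | 0.45 |
| Power, marginal robust logit | 0.69 | 0.59 | 0.48 |
| Null rejection, pseudo-likelihood | 3.6% | 1.9% | 0.6% |
| Null rejection, quadrature | 5.1% | 4.1% | 3.7% |
| Null rejection, marginal robust logit | 5.6% | 5.0% | 4.8% |
| Pseudo-likelihood log-OR (subject-specific value 1.50) | 1.27 | 0.99 | 0.80 |
| Population-averaged log-OR | 1.25 | 0.91 | 0.69 |

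At 40 per arm, power at SD 1, 2 and 3 is 0.50, 0.26 and 0.15 for pseudo-likelihood, against 0.56, 0.43 and 0.33 for the marginal logit.

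The mechanism is the standard error. In a separate null simulation the mean model SE was 0.556 against an empirical SD of 0.470 at SD 2, and 0.576 against 0.426 at SD 3: ratios of 1.18 and 1.35. A two-sided 5% test with 118 df then rejects about 2(1 − Φ(1.98 × 1.18)) = 1.9% and 2(1 − Φ(1.98 × 1.35)) = 0.7% of the time; the simulated rates were 1.7% and 0.5%.

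Part of the fall in power across the table comes from holding the subject-specific effect fixed while the population-averaged effect shrinks. With marginal Week 4 risks fixed instead at 0.4 and 0.6, pseudo-likelihood power is flat (0.31, 0.32, 0.34), while the marginal logit rises (0.40, 0.51, 0.62). The cost of the method is the gap between methods, not the decline across SD.

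**Threshold against days.** Someone who goes from 0 to 6 days of non-combustible use, with no combustible use, scores 0 at both occasions in both fitted models, under either meaning of combined days. Illustrative power (60 per arm, 2,000 runs, cut tested by the marginal logit), for baseline shares at 0 / 1-6 / 7 days:

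| VLNC uptake pattern | 50/10/40%: cut, days | 65/10/25%: cut, days |
|---|---|---|
| 30% of non-daily users become daily | 0.76, 0.73 | 0.89, 0.90 |
| Half of that uptake daily, half 1-6 days | 0.31, 0.53 | 0.47, 0.74 |
| 30% of non-users take up 1-6 days | 0.05, 0.30 | 0.04, 0.48 |

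**The case against.** Four objections have force.

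First, no error-rate harm is shown for the SAP as worded. All the power and rejection figures belong to a logit link that the SAP never names. A reader might infer that the primary ATP test is known to be conservative. The documents do not support that: it requires both that log is a slip and that the subject SD is around 2 or more. Peaks at 0 and 7 hint at stable habits, but no variance is reported.

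Second, the two readings do not add up. In simulated logit data, a log-link pseudo-likelihood fit succeeded in 85-92 of 100 data sets at SD 1, 23-52 at SD 2 and 2-21 at SD 3. The SAP reports non-convergence only for combustible use. So if the link really was log and the model fitted, a small SD is more likely; if it was a slip, the problem of probabilities above 1 disappears.

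Third, a reader might infer that the planned ATP analyses could never register part-week use. That fails if combined days is a 0-14 sum: 4 non-combustible plus 3 combustible days would score 1 without daily use. Rare combustible use at Week 4 limits how often this happens. Nor is a sensitivity analysis missing altogether; what is missing is one on days. The SAP does give reasons for the cut, and where uptake is daily the cut loses nothing.

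Fourth, the SAP is written in the past tense and reports fitted models. Swapping the primary estimator now would be a change made after the results were known.

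All four stand as limits on the claim. They do not supply the missing link, estimand, definition of combined days or days analysis.

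**Conclusion.** The point holds in a conditional form. The stated combination of link, random effect and estimation method is unsatisfactory on either reading. As a literal log link it permits probabilities above 1 (about 2-8% of people at mean prevalence 0.4 and log-scale SD 0.5-1; at most about 2% at 0.2), with no direction of bias established. As a logit link it is conservative rather than invalid. Its power shortfall against a marginal robust logit is 0.07 at SD 1 (0.69 − 0.62), 0.17 at SD 2 (0.59 − 0.42) and 0.25 at SD 3 (0.48 − 0.23), for a large assumed effect (62% against 40% at Week 4 when SD is 2). Prevalence, variance, effect and final N are assumptions; only the 60 per arm comes from the SAP, as a target that was not met.

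The absence of any fitted ATP analysis in days is a matter of record. Its importance depends on the uptake pattern, from no loss to a cut with no power beyond chance. This should be fixed, but it does not invalidate the primary analysis.

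**What to change.** 1. State the link actually used and the estimand: risk ratio, subject-specific odds ratio or population-averaged odds ratio. If log is a slip, correct it in items 2 and 3.
2. Re-fit both binary ATP outcomes with a logit link by adaptive quadrature (METHOD=QUAD in PROC GLIMMIX), or with a marginal logit and robust standard errors. Report this beside the existing pseudo-likelihood result, labelled as specified after the data were seen; do not silently replace the primary. If the fitted link was literally log, or any fitted probability exceeded 1, say so and base the interpretation on the logit fit.
3. Keep the 7+ cut as primary and state whether combined days is a 0-14 sum or days with any ATP use (0-7).
4. Add one sensitivity analysis of days with any ATP use (0-7) from the TLFB, using the SAP's 2 × 2 mixed model with sandwich standard errors or a bootstrap interval.
5. Do not read a non-significant ATP result as evidence of no substitution without these checks.

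The cost is SAP wording and a re-run on data in hand. There are downsides:
- Odds ratios replace risk ratios.
- Quadrature leans on a normal subject effect, which peaks at 0 and 7 may strain. Its null rejection was 2.8-5.1% in 1,000-run scenarios but reached 6.8% in a 400-run check. The marginal test reached 7.1% at SD 4 with 40 per arm.
- An unweighted marginal model needs more than missing-at-random. With an independence working correlation and dropout that depended on baseline status differently by arm (about 20% missing), its log-OR was off by −0.07, −0.16 and −0.22 at SD 1, 2 and 3, while quadrature was not off.
- The added analyses come after the results.
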